### Sample

The study involves about 170 UMA and URM  $> 8$  years.

Recruitment involved inviting reception centers and municipalities from all over Norway to participate as a first step. The children in the centers and municipalities that accepted to participate who spoke Pashto, Dari, Arabic, Somali or Tigrinya, were then invited to

participate (see information below).

A total of 18 TRT-groups have been conducted during the project period. To avoid cross-contamination [37] of the intervention, the children were allocated to Intervention or Control groups on an institutional level. We endorsed half of the participating reception centers and resettlement municipalities to Intervention Groups, and the other half to wait-list Control Groups. We did this based on practical considerations related to the data collection, such as time frames of the commission, geographical location of the targeted centers and municipalities, and availability of bilingual research assistants. The Intervention Groups started the TRT soon after the information meeting, and the Control Groups started when they had completed the five weekly sessions and the W2 data collection.

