## Teaching Recovery Techniques: An Effective Short-term Intervention

Teaching Recovery Techniques (TRT) is a manualized, short term, group based intervention, which specifically focuses on children's symptoms of PTSD. TRT was developed by experts of the Children and War Foundation (C&W; [www.childrenandwar.org](http://www.childrenandwar.org)) to heal children's mental reactions to war and disaster-related trauma [29]. The aim of the intervention is to teach children self- help methods, by increasing perceptions of control and self-efficacy in relation to trauma symptoms, based on recommended and evidence based CBT- methods for trauma relief. The five sessions help students to understand the causes of trauma and recognize signs and symptoms. Adolescents are taught a range of coping skills to stop flashbacks and other intrusive images, sounds, or smells. Student hyperarousal is addressed through stabilization and relaxation techniques, and phobic avoidance behavior is gradually desensitized through use of relaxation with anxiety and anger hierarchies.

The program is delivered to groups of 5 - 15 adolescents by local group-leaders in pairs that are trained by representatives from C&W.

TRT has proven to be effective in reducing trauma-related mental health symptoms in contexts of war and disaster when delivered by non-clinicians and "lay" people [30-35]. However, TRT has rarely been implemented with UMA or URM in post-war contexts, who have a longer time span since the traumatic exposure than children in contexts of war, and who are experiencing additional psychosocial challenges. A small study conducted in the

U.K., showed more beneficial mental health effects among refugees than asylum-seekers, and the authors speculated if experiences of post-migration stressors might have reduced the effectiveness in the latter group [36]. A small pilot study in Sweden yielded positive effects of TRT among 48 UMA and URM.

In spite of the focus of TRT to increase coping and self-efficacy, none of the above mentioned studies included any measures of QoL-related constructs. To enhance our knowledge of the effectiveness of TRT in post-war contexts, we expand on the designs of the referred studies by 1) including a wait-list control group; 2) examining longer term effects; 3) including QoL-related outcomes (subjective wellbeing and self-efficacy) in addition to symptoms of PTSD, and 4) taking the psychosocial context into consideration.

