## Aims

The overall aim is to evaluate the effectiveness on mental health of TRT among unaccompanied minor asylum-seekers and refugees.

More specifically, we will:

Examine the short and long-term effectiveness of TRT in reducing mental health symptoms and promote QoL

- *Primary hypothesis:* The TRT intervention is expected to significantly improve the mental health status (i.e. alleviate symptoms of post-traumatic stress disorder, depression and anxiety and promote QoL) compared to the waiting-list control group.
- *Secondary hypotheses:* 1) Asylum- related and post-resettlement psychosocial stressors predict mental health problems and QoL over and above pre-migration traumatic exposure. 2) Asylum-related and post-resettlement psychosocial stressors predict variation in the short and long term effects of the effect of the TRT.

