### Power

Several power analyses have been performed to calculate the required sample size, given an  $\alpha$ -level of 0.05 and power ( $1-\beta$ ) of 0.80. The analyses show that a sample of  $n=150$  will be sufficient to detect standardized regression effects of 0.20 or larger. For intervention effects there will be power to detect effect sizes of  $d=0.40$  or larger. With use of linear mixed effect models and structural equation modelling, and the wait-list design, power will be even higher. Thus, we are confident that the planned sample size is sufficient to address the research questions posed.

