### **Procedures**

Treatment response was registered by self-report questionnaires administered before upstart of TRT (W1), two weeks after the completion of TRT (W2) and two months after completion of TRT (W3). The questionnaires were translated to the participants' respective languages by standardized back-translation procedures. The children filled in the questionnaires in a group setting. The trained bilingual research assistants read the questions to the children, and assisted them with language issues.

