### Statistical Analyses

Treatment effects will be analyzed using ANCOVA and mixed regression models that may be flexibly adjusted according to the dependency structure in the repeated data.

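### The design as described supports a wait-list-controlled comparison at W2 only, but the plan does not limit it to W2 or say how the long-term effect is to be identified

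*Combined protocol and SAP*

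**What the plan says.** All references are to the combined protocol and SAP.

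- **Aims.** The stated aim is "Examine the short and long-term effectiveness of TRT in reducing mental health symptoms and promote QoL". The primary hypothesis beneath it expects improvement "compared to the waiting-list control group" and names no wave. Secondary hypothesis 2 is that psychosocial stressors "predict variation in the short and long term effects of the effect of the TRT".
- **Sample.** Intervention groups began TRT soon after the information meeting; "the Control Groups started when they had completed the five weekly sessions and the W2 data collection". No minimum or actual wait after W2 is given.
- **Procedures.** After a baseline at W1, the follow-up waves are placed "two weeks after the completion of TRT (W2) and two months after completion of TRT (W3"). The control arm's own dates are not given.
- **Statistical Analyses.** The section is one sentence. It names ANCOVA and "mixed regression models that may be flexibly adjusted according to the dependency structure in the repeated data". It gives no contrast, no time point and no rule for controls who have since received TRT.
- **Teaching Recovery Techniques: An Effective Short-term Intervention.** The advances over previous studies are listed as "1) including a wait-list control group; 2) examining longer term effects", that is, as two separate items.

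**The concern.** A wait-list arm gives an untreated comparison only while it is waiting. Here the waiting may end as soon as W2 has been collected, whereas the aim and secondary hypothesis 2 extend to the long term. An analyst who follows the text could fit arm by wave to all three waves and report either the W3 arm difference or one averaged over W2 and W3 as the effect of TRT against the waiting list. If controls have been treated in the meantime, that number compares TRT given early with TRT given later. A benefit that lasts could then appear as little or no effect. In the other direction, uncontrolled change in the intervention arm could be presented as a controlled long-term effect, because the plan does not separate the two.

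**Working it through.** The plan states neither the W2-to-W3 gap nor the control wait, so there is no figure of its own to reproduce. The check is timeline arithmetic.

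**Inputs.** Five weekly sessions, and a control start after W2 (Sample). W2 at two weeks and W3 at two months after completion (Procedures). Assumption: two months is 8.0 weeks (56 days) to 8.9 weeks (62 days).

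**Gap between waves, intervention arm.** Gap = two months − two weeks = 8.0 − 2 to 8.9 − 2 = 6.0 to 6.9 weeks.

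**Control exposure at the intervention arm's W3.** Let *d* be the weeks from W2 to the controls' first session. Sessions fall at *d*, *d*+1, *d*+2, *d*+3 and *d*+4 weeks after W2. The number received is the count of *k* in 0 to 4 with *d* + *k* ≤ gap. The result is the same for gaps of 6.0 and 6.9 weeks:

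| Delay *d* after W2 (weeks) | Sessions received, of 5 |
|---|---|
| 0, 1 or 2 | 5 |
| 3 | 4 |
| 4 | 3 |
| 5 | 2 |
| 6 | 1 |
| 7 or more | 0 |

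- All five sessions are complete if *d* ≤ gap − 4 = 2.0 to 2.9 weeks. If the course is counted as five full weeks, the limit is gap − 5 = 1.0 to 1.9 weeks.
- No session has been received only if *d* exceeds the gap, 6.0 to 6.9 weeks.
- With *d* = 0, controls are 6.0 − 4 to 6.9 − 4 = 2.0 to 2.9 weeks past their last session. That is about the point at which the intervention arm was measured at W2.

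**If control W3 runs on the controls' own clock.** It falls at *d* + 4 + 8.0 to *d* + 4 + 8.9 = *d* + 12.0 to *d* + 12.9 weeks after W2. That is *d* + 6 weeks later than the intervention arm's W3, and every control who completed the course has had all of it.

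**If controls have no W3.** There is nothing to compare with.

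**What a W3 arm contrast would estimate.** Leave aside arm differences from other causes. Let *L* be the effect two months after TRT and *g* the gain that controls already have from their own TRT when measured. The contrast is *L* − *g*. It equals *L* only when *g* = 0, which needs the long wait above. With own-clock W3 in both arms and equal effects, *g* = *L* and the contrast is *L* − *L* = 0, however large *L* is. An estimate pooled over W2 and W3 mixes this quantity with the W2 contrast.

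**The case against.** The best defence is that nothing wrong has been planned. No section calls for an arm test at W3. The wait-list control and the longer-term effects are listed as separate advances, which would fit a controlled W2 comparison followed by uncontrolled follow-up. The control start after W2 is openly stated, and a group that has begun TRT is no longer on a waiting list. The document is a PhD proposal within a larger approved study (Ethical Aspects), whose protocol may set out the schedule.

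Much of this stands. The harm arises only if a contrast that the plan does not spell out is fitted and interpreted as TRT against no treatment. But the intended reading is written nowhere: the hypothesis against the waiting list sits under an aim that includes the long term, and the analysis sentence covers the repeated data without restriction.

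Three stronger readings are tempting, and the documents do not support them:

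- *That controls had certainly completed TRT by the intervention arm's W3.* The wait after W2 is not given, so the extent of exposure cannot be fixed.
- *That the W2 comparison is affected too.* The word for those who had completed the sessions in "the Control Groups started when they had completed the five weekly sessions and the W2 data collection" is ambiguous, but either reading puts the control start after the W2 data collection. This point gives no ground for doubting W2.
- *That the Power section shows a pooled arm contrast is intended.* It says "With use of linear mixed effect models and structural equation modelling, and the wait-list design, power will be even higher", but not how the wait-list design adds power. The authors may equally mean to use the controls' later treated data.

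**Conclusion.** The point holds as a gap in the definition of the comparison, and it should be closed before results are interpreted. As described, the design supports TRT versus no treatment at W2 only. At the intervention arm's W3, controls would have had all five sessions if they started within about two weeks of W2, and some of them if they started later but within about 6 to 7 weeks. Only a longer wait, which is not described, would leave them untreated. On the other two possibilities, own-clock W3 or no W3, there is no untreated comparator at all.

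The conclusion rests on weekly sessions being held as stated, on two months meaning 8.0 to 8.9 weeks, and on no long wait being documented elsewhere. It does not say that a W3 arm test is planned; it says that the plan does not rule one out.

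**What to change.** 1. State in Aims and in Statistical Analyses that the comparison with the waiting-list control is the W2 contrast adjusted for W1, which the ANCOVA already named can provide. Report the control arm's actual wave dates and TRT start dates.
2. State that an arm contrast at W3, or one pooled over W2 and W3, will not be interpreted as TRT versus no treatment.
3. Report change from W2 to W3 in the intervention arm as uncontrolled follow-up, open to time trends.
4. Apply the same limit to the long-term part of secondary hypothesis 2: an association between stressors and later change in the intervention arm is not evidence that stressors alter a controlled long-term effect.

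The cost is a change to the wording of the aims and one analysis rule. No new data are needed; the Progress Plan lists data collection as completed, so the dates have only to be reported. The real price is scientific: the long-term claim becomes uncontrolled.

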### **Overview of the recruitment process**

Invitation to participate in the study was sent to reception centers and resettlement municipalities, and health nurses of the local primary health care, based on contact information from the three commissioning directorates. Centers / municipalities that agreed to participate assigned a contact person that assisted the research team in the information and recruitment stages of the project. They typically approached the largest language groups in their respective institutions. The research team sent out brief, written information and sound tracks about the project in the respective languages to the children, with an invitation to attend an information meeting. We also invited their legal guardians (representatives), and the TRT-group leaders to the information meeting, where we presented the intervention and the project, with the support of bilingual research assistants in the role as translators.

### **Inclusion – exclusion criteria**

Inclusion criterion was based on the children fulfilling criteria indicative of PTSD on the Children's Revised Impact of Event Scale (CRIES-8), that is, a score  $\geq 17$  on intrusion and avoidance subscales [38]. Thus, at the end of the information meeting, we asked the children who were interested in participating in the study to fill in the checklist, which we provided both in the five foreign languages and in Norwegian. The bilingual research assistants read the questions in the children's mother tongue.

The names of the children who qualified to receive the intervention were then given to the group leaders, who finalized the recruitment.

Exclusion criteria involved known serious medical condition such as mental disabilities and psychotic disorder.

All legal guardians of the invited unaccompanied minors  $< 16$  years signed a consent form. Children  $\geq 16$  years signed the consent form on their own behalf, but their legal guardians were informed about the project, and encouraged to discuss it with the child they represented.

### **Procedures**

Treatment response was registered by self-report questionnaires administered before upstart of TRT (W1), two weeks after the completion of TRT (W2) and two months after completion of TRT (W3). The questionnaires were translated to the participants' respective languages by standardized back-translation procedures. The children filled in the questionnaires in a group setting. The trained bilingual research assistants read the questions to the children, and assisted them with language issues.

## Measures

The included measures have demonstrated good psychometric properties in previous studies of mental health among children of war and disaster, including in TRT effect-studies. They have shown good psychometric properties in former studies in different cultures or involving multi-ethnic groups in Norway.

### Mental Health Outcomes

**Symptoms of PTSD:** Children's Revised Impact of Event Scale, CRIES-8 (31, 39) with eight items of intrusion and avoidance was used for screening purposes, and CRIES-13 (42) with additional five hyperarousal items was used at W1, W2 and W3 [30, 39].

**Qualitive of Life:** 1) **Subjective Well-being:** Cantril Ladder [40]. The participants are presented with an illustration of a ladder with ten steps, and informed that the best possible life for them being on step 10, and the worst possible life being a 0. 2) **Perceived Self-Efficacy:** was measured by a short version of five items of The Generalized Self-Efficacy scale, GSE [41] that has previously been used with immigrant populations in Norway [42].

### Predictors

**Traumatic events:** 20 items developed in collaboration with the user groups.

**Asylum-related stressors:** 1) Length of asylum process + status of the asylum application, and 2) 13 stressors related to network problems and the psychosocial context in the centers that was developed in collaboration with the user group

**Post-resettlement stressors:** short version of a daily hassles scale developed by the NIPH for studies of mental health in immigrant and refugee background youth populations [16].

**Child demographic background variables:** age, gender, country of origin, length of stay in Norway.

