## Mental health, trauma and psychosocial stressors

The World Health Organization (WHO) defines mental health as a state of well-being in which every individual realizes his or her own potential, can cope with the normal stresses of life, can work productively and fruitfully, and is able to make a contribution to her or his community [12]. In its most recent Strategy of good mental health [13], the Government describes mental health as including good mental health, quality of life, mental health problems and mental health disorders. Quality of life (QoL) involves a range of different positive experiences such as happiness, safety, affiliation, coping, and meaningfulness (p. 9),

---

 *Unaccompanied minor asylum-seekers* (UMA) are children below 18 years of age, who travel without the company of an adult legal caretaker to seek asylum in a foreign country. We distinguish this group from *unaccompanied refugee minors* (URM), who are former UMAs that have been granted asylum and are resettled in municipalities. We refer to them as refugees even if protection was conceded for humanitarian or other reasons rather than to shield from persecution, imprisonment etc.

and is conceptualized in a variety of ways [14]. In the present study, QoL refers to perceived subjective wellbeing and self-efficacy.

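### The pooled n=150 behind the detectable regression effect of 0.20 does not carry over to the post-resettlement stressor scale, which by the plan's own definitions applies only to resettled children

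*Combined protocol and SAP*

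**What the plan says.** **Power.** At a two-group level the section is brief: alpha 0.05, power 0.80, and a sample of 150 that "will be sufficient to detect standardized regression effects of 0.20 or larger". It gives one pooled figure, with no sidedness, no covariates and no split by type of child. It then concludes that the planned size is enough for the questions asked.

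**Sample.** "The study involves about 170 UMA and URM", recruited from both reception centers and municipalities. The numbers of UMA and URM are not stated.

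**Background, section on mental health, trauma and psychosocial stressors.** The footnote separates UMA from URM, "who are former UMAs that have been granted asylum and are resettled in municipalities". The text of the same section places post-resettlement stressors in the period after residence has been obtained.

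**Aims.** Secondary hypothesis 1 expects that asylum-related and "post-resettlement psychosocial stressors predict mental health problems and QoL over and above pre-migration traumatic exposure". Secondary hypothesis 2 uses the same stressors to explain variation in the effect of the intervention.

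**Predictors.** Asylum-related stressors consist of length of process and application status, plus "13 stressors related to network problems and the psychosocial context in the centers". Post-resettlement stressors are measured by a short daily hassles scale. The section does not say which children answered which scale.

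**Statistical Analyses.** The one sentence there concerns treatment effects. It gives no model for the stressor hypotheses.

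**The concern.** A child still awaiting a decision has no post-resettlement experience, so this predictor is undefined for every UMA in the sample. The Power section nevertheless offers one pooled sample size for regression effects and draws its conclusion for all the questions, including the two stressor hypotheses. The number of children who can inform the post-resettlement slope is the number of URM, which must be smaller than the total.

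At stake is how a weak or null stressor result will be read. A reader who trusts the stated figure would take a non-significant slope as evidence against an effect of 0.20, when the study may have had about an even chance, or less, of detecting it. Secondary hypothesis 2 relies on the same scale and inherits the problem. The primary treatment comparison is not affected.

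**Working it through.** **Inputs from the documents.** Alpha 0.05, power 0.80, n=150, standardized effect 0.20 (Power); about 170 children (Sample). **Not stated, so assumed:** sidedness (both shown), the UMA:URM split (a range is shown), no clustering and no attrition.

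**1. Reproduce the plan's figure.** Fisher z for one standardized slope, with atanh(0.20) = 0.2027:

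n = ((z_alpha + z_power) / atanh(0.20))² + 3

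- Two-sided: ((1.960 + 0.842) / 0.2027)² + 3 = 194. Power at n=150 is 69%.
- One-sided: ((1.645 + 0.842) / 0.2027)² + 3 = 153.4, so 154. Power at n=150 is 79%.

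The plan's 150 is therefore close to a one-sided calculation. It can also be reached two-sided if other predictors explain variance. With f² = 0.20² / (1 − R²other − 0.20²) and noncentrality f²·n, R²other = 0.206 gives f² = 0.04 / 0.754 = 0.053. The noncentrality at n=150 is then about 8.0 and power is 80%. This variant takes the stressor score as uncorrelated with the other predictors. The plan states neither convention.

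**2. How many children can inform each scale.** 170 − 150 = 20, so the post-resettlement scale reaches 150 only if 20 or fewer children are UMA. If the center items were answered by UMA only, the two scales have no respondents in common. Having 150 on each would then need 2 × 150 = 300 children against about 170. At least one scale is short, and both are unless one group has 150 or more.

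**3. Power and detectable effect at the smaller n.** Power = Φ(atanh(0.20)·√(n − 3) − z_alpha); detectable effect at 80% power = tanh((z_alpha + z_power) / √(n − 3)). For example, at n=85 two-sided: 0.2027 × √82 − 1.960 = −0.124, giving 45%; and tanh(2.802 / 9.055) = 0.30.

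| Children on the scale (share of 170) | Power, two-sided | Power, one-sided | Power, two-sided, R²other = 0.206 | Detectable effect, two-sided / one-sided (Fisher z) |
|---|---|---|---|---|
| 136 (80%) | 65% | 76% | 76% | 0.24 / 0.21 |
| 119 (70%) | 59% | 71% | 70% | 0.25 / 0.23 |
| 85 (50%) | 45% | 58% | 56% | 0.30 / 0.27 |
| 51 (30%) | 29% | 41% | 36% | 0.38 / 0.34 |

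**4. Separate the effect of the split from the choice of convention.** A plain two-sided test has only 69% power at n=150, so part of the gap from 80% has nothing to do with the split. Within each convention, going from 150 to 85 children takes power from 69% to 45%, from 79% to 58%, or from 80% to 56%: a loss of 21 to 24 points.

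**The case against.** The strongest case against is that the documents do not say who answered what. URM are former UMA, so they could have reported center stressors in retrospect. Length of asylum process can be recorded for both groups, and network problems are not obviously confined to centers. The asylum-related set could therefore have the full sample. This stands. A reader might infer that neither scale has 150 children; that depends on an unstated split and on the absence of retrospective answers, and the documents establish neither.

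A reader might also infer that a single model with both scales would lose most or all cases, or that filling the inapplicable scale with zeros would confound stress with legal status. The plan contains no such model and no such coding. The Aims name two stressor types in one sentence, and Statistical Analyses deals with treatment effects only. Those harms are hypothetical. If URM answered both scales, a joint model would keep all URM.

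The hassles scale is described as built for immigrant and refugee youth generally, so UMA may have filled it in. That would not rescue the stated n, because their answers would not describe the post-resettlement experience named in the hypotheses.

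Finally, hypothesis 1 concerns an effect beyond trauma exposure, and covariates can raise power above the bare Fisher z figures. This is fair, and the R² column allows for it. The shortfall is smaller but remains: about 56% at n=85. Clustering by center or municipality and attrition work in the other direction; the documents give no figure for either.

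**Conclusion.** The point holds for the post-resettlement scale. A pooled n is credited to a predictor that the plan's own definitions restrict to part of the sample. Unless URM make up at least 150 of about 170 children, the stated sample is not there for that slope. At an assumed even split, power for 0.20 is 45% to 58% depending on convention, and the Fisher z detectable effect is 0.27 to 0.30 rather than 0.20. With 119 URM, power is 59% to 71%; with 51 it is 29% to 41%.

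For the center items the conclusion is conditional: they are short only if UMA alone answered them and UMA number fewer than 150. All figures rest on an assumed split of 170 and on no clustering or attrition. The matter concerns a stated power figure for secondary hypotheses, and the correction is cheap.

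**What to change.** In Power, keep the pooled statement only for predictors defined for every child. For the post-resettlement scale, give the effect detectable with 80% power at the actual number of URM. Do the same for the center items at the number of UMA, if only UMA answered them. State the sidedness and any variance assumed to be explained by other predictors.

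In Predictors, state which children answered each scale and how many. In Statistical Analyses, say how each scale enters the stressor models. Estimating each effect among the children to whom the scale applies is one sound option. Another is a prespecified score standardized within group, with UMA/URM status as a covariate. The full sample stays in use for predictors that everyone has.

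The cost is a less favourable stated figure and a little more analysis. The Progress Plan lists data collection as completed, so the counts should be available to the team, and no further recruitment is needed.
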